Penicillin remains a reliable class of antibiotic that addresses majority of infections both in outpatient and inpatient settings. ^{1,2} It is also one of the cheapest antibiotics to use for empiric therapy for susceptible infections. ^{3,4} Emerging literature suggests that the number of patients with historical penicillin allergy is an overestimate. A growing number of studies show that only approximately 10 % of patients with historical penicillin allergy are truly allergic after verified allergy testing is done. ^{1-3,5,7} Despite this, efforts on antibiotic allergy delabeling remains sparse and penicillin allergy remains to be the most common drug allergy reported.

Moreover, few institutions have validated, much less implemented, protocols to determine truly allergic patients who have reported penicillin allergy when diagnosed with infections theoretically susceptible to penicillin.⁶ One limitation perhaps is the absence of validated questionnaire that uniformly captures accepted levels of risk especially in the pediatric population.⁷ As a result, these patients end up receiving alternative antimicrobial agents that pose a risk for emergence of resistance, development of

unnecessary intestinal dysbiosis and increased economic burden to health care resulting in suboptimal clinical outcome. ¹⁻⁶

Thus, identifying patients with no immunologically-mediated penicillin allergy and delabeling them in the electronic medical record (EMR) accordingly will mitigate the use of second-line antibiotics, aid in minimizing development of resistance, ameliorate unnecessary economic burden and overall lead to positive impact in clinical outcome and patient care. In the same way, this process will also identify patients with true penicillin allergy creating a point-of-care opportunity to provide them proper guidance on the importance of Allergy/Immunology followup for further evaluation and management.

Inclusion and Exclusion Criteria

	Inclusion Criteria for screening
1.	Patients 3-18 years old admitted at Rainbow 3, 5 and 6 with penicillin allergy label on EMR identified through TheraDoc database (including patients admitted for
	antibiotic therapy for an infection)
2.	Patients with available parent/s or legal guardian who can give both written and verbal consent to the oral challenge testing
3.	Patients with available parent/s or legal guardian during the conduct of oral amoxicillin challenge testing
	Inclusion Criteria for oral challenge test

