1.	Patients who will be identified as low-risk patients based on the standardized screening questionnaire. Low-risk group patients are those patients with previous reaction not suggestive of anaphylaxis AND not requiring hospitalization for the reaction OR reaction considered non-immunologic (e.g. diarrhea, nausea, yeast vaginitis) OR exposure to penicillin-containing antibiotic after the date of reported reaction with no anaphylaxis and hospitalization AND no serious types of delayed reactions such as Steven-Johnson syndrome (SJS), toxic epidermal necrolysis (TEN), acute interstitial nephritis (AIN), drug-induced hepatitis or other documented organ injury, drug rash eosinophilia systemic symptoms (DRESS), hemolytic anemia, drug-induced cytopenia, and serum sickness. Patients who had delayed reaction (onset more than 24 hours) of isolated, non-progressive

symptoms (such as rash/hives alone) also belong to this group.

	Exclusion Criteria for screening
1.	Patients who cannot tolerate amoxicillin by enteral route.
2.	Patients with no parents or legal guardian available to give both written and verbal consent to the oral challenge testing
3.	Patients with no available parents or legal guardian during the conduct of oral amoxicillin challenge testing
4.	Patients currently on antihistamine or have received antihistamine in the previous 48 hours
5.	Patients who are critically ill or unable to complete challenge testing due to intercurrent illness
6 .	Patients who have been vomiting more than twice in the past 24 hours or are actively vomiting
7.	Patients with respiratory symptoms warranting oxygen therapy or pulmonary finding of wheezing or stridor
8.	Patients identified as having anaphylactic reaction to penicillin in the EMR through TheraDoc system.

	Exclusion Criteria for oral amoxicillin challenge testing
1.	Patients who will be identified as no-risk patients based on the standardized
	screening questionnaire. No-risk group patients are those patients who are
	historically labeled with penicillin allergy in the EMR based on family history
	alone OR those who have tolerated penicillin after a concerning incident without
	any reaction OR with penicillin allergy label but deny any history of reaction to
	any form of penicillin on screening questionnaire
2.	Patients who will be identified as high-risk patients based on the standardized
	screening questionnaire. High-risk group patients are those patients with penicillin

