This step is subdivided into two graded steps: administration of 10% of the standard dose followed by administration of 90% of the rest of the standard dose separated by 30 minutes time interval (see Appendix D).

Administration of 10% of standard dose:

A set of baseline vital signs will be obtained by a trained study team member before initiation of step-wise amoxicillin oral challenge allergy testing. If vital signs are normal and no apparent contraindication to perform the test is identified, the testing will be commenced.

Patients will first receive 10% of the standard drug dose in the form of enteral amoxicillin (see Appendix D). A trained study team member will administer the oral amoxicillin dose and closely monitor and observe patients for 30 minutes at the bedside following dose administration for any sign or symptom of drug reaction.

At any point the patient will have any reaction to the initial 10% dose, testing needs to be stopped immediately. A trained study team member needs to assess the patient right away at bedside and should consider giving diphenhydramine by mouth (or by IV or IM as clinically applicable) if reaction does not meet criteria for anaphylaxis (see definition of terms – attached document). Diphenhydramine will be available at bedside prior to initiation of the oral amoxicillin challenge testing. Administration of diphenhydramine will be done by the study team member. The patient needs to be monitored for the next 2 hours postadministration of diphenhydramine for the progression of symptoms. The reaction needs to be documented in the patient's chart specifying the reaction observed and intervention given (see Appendix C.3).

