If the patient develops any symptom indicative of anaphylaxis (see definition of terms), epinephrine will be administered right away either by IV or IM (see Appendix D) and a rapid response alert or code will be called as indicated. Epinephrine will be available at bedside prior to initiation of oral challenge testing. Administration of epinephrine will be done by a trained study team member. Inhaled albuterol or supplemental oxygen will be administered if indicated. Administration of both will also be done by the study team member with the assistance of the patient's nurse. The event needs to be documented in the patient's chart specifying the reaction and the intervention given (see Appendix C.3). The patient will need to be monitored for progression of symptoms for the next 2 hours post-administration of epinephrine so a proper disposition can be made (remain on the floor or transfer to higher level of care)

Any patient who develops any type of reaction at any point during the administration of the initial 10 % dose will be labeled to have failed the test. This will also be documented in the patient's chart accordingly. The patient's penicillin allergy status will then be retained in the chart (see Appendix C.3). The patient will be provided proper guidance and recommendation to follow up with an allergist for further evaluation and management.

Administration of the remaining 90% of standard dose:

If the patient did not develop any reaction to the 10% initial oral dose of amoxicillin following 30 minutes of administration, another set of vital signs will then be obtained by a trained study team member. If vital signs are normal, then the patient can proceed to receive the remaining 90% of the test standard dose of amoxicillin (see Appendix D). A trained study team member needs to be present at bedside for 30 minutes following the administration of the rest of the 90% of the dose. Another set of vital signs will be obtained 30 and 60 minutes following the administration of the rest of the 90% of the dose.

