Administration of the remaining 90% of standard dose: If the patient did not develop any reaction to the 10% initial oral dose of amoxicillin following 30 minutes of administration, another set of vital signs will then be obtained by a trained study team member. If vital signs are normal, then the patient can proceed to receive the remaining 90% of the test standard dose of amoxicillin (see Appendix D). A trained study team member needs to be present at bedside for 30 minutes following the administration of the rest of the 90% of the dose. Another set of vital signs will be obtained 30 and 60 minutes following the administration of the rest of the 90% of the dose.

If the patient develops any symptom indicative of anaphylaxis (see definition of terms), epinephrine will be administered right away either by IV or IM (see Appendix D) and a rapid response alert or code will be called as indicated. Epinephrine will be available at bedside prior to initiation of oral challenge testing. Administration of epinephrine will be done by a trained study team member. Inhaled albuterol or supplemental oxygen will be administered if indicated. Administration of both will also be done by the study team member with the assistance of the patient's nurse. The event needs to be documented in the patient's chart specifying the reaction and the intervention given (see Appendix C.3). The patient will need to be monitored for progression of symptoms for the next 2 hours post-administration of epinephrine so a proper disposition can be made (remain on the floor or transfer to higher level of care)

Any patient who develops any type of reaction at any point during the administration of the remaining 90 % of dose will be labeled to have failed the test. This will also be documented in the patient's chart accordingly (see Appendix C.3). The patient's penicillin allergy status will then be retained in the chart. The patient will be provided proper guidance and recommendation to follow up with an allergist for further evaluation and management.

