The conduct of the challenge testing will be done only from 8:00 AM - 2:30 PM to ensure availability of full attendance of medical staff in the event untoward issues occur. The single visit from consent to the time amoxicillin oral challenge is done will take an average of approximately 3 hours. Enrollment and conduct of the study will be done over a 6-month period (September 22, 2021 – March 31, 2022).

Data to be Collected for your study

(AFTER consent and HIPAA Authorization have been obtained)

Data that will be collected will include patient's name, date of birth, age, sex, MRN, race (if available), penicillin allergy status (reaction description if stated), PCP's name, PCP's contact information, and the responses of parent/s or legal guardian to the screening questionnaire (see attached Appendix B)

Data Analysis Plan

Descriptive statistical tools will be used to analyze the data. A P-value of of <0.05 will be used to determine statistical significance in the result interpretation.

The primary end point will be verification of patients' penicillin allergy status through direct oral challenge testing with amoxicillin.

Secondary endpoints will be:

- 1. Identification of patients (no-risk patients and low-risk patients who passed the oral challenge testing) who will then be delabeled in the EMR.
- 2. Identification of patients (no-risk patients and low-risk patients who passed the oral challenge testing) in order to provide proper guidance to their PCPs regarding use of penicillin in the future.
- 3. Identification of high-risk risk patients and low-risk patients who failed the oral amoxicillin challenge testing in order to provide them proper guidance on referral to allergy/immunology for further evaluation and management.

Risks to Research Participants

Reasonable foreseeable risks include breach of confidentiality, discomfort, inconveniences both to parent/s or legal guardian and patients. These will be protected against through observance of HIPAA-concordant practices in the conduct of the study as well as efficient and timely performance of challenge testing to avoid consuming too much of patients' time.

Reaction to the intervention is also one of the foreseeable risk to the patients in this study. Potential reactions to the intervention (amoxicillin challenge testing) include skin rash, nausea, vomiting, diarrhea, and very rarely anaphylaxis.

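### Challenge failure is a single undifferentiated class with no baseline symptom record, so the failure proportion cannot be read as a proportion with true penicillin allergy

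*Combined protocol and SAP*

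**What the plan says.** **Failure rule.** Step 6 of Study Procedures Methods has one failure class at each dose step. For the first dose: "Any patient who develops any type of reaction at any point during the administration of the initial 10 % dose will be labeled to have failed". For the second dose, the same applies to "Any patient who develops any type of reaction at any point during the administration of the remaining 90 % of dose". The allergy label then stays in the chart and the child is advised to see an allergist. A child with no reaction by 120 minutes from the start of the challenge is deemed not allergic.

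**Meaning of a GI event.** The inclusion criteria for the oral challenge place in the low-risk group a child whose earlier event was a "reaction considered non-immunologic (e.g. diarrhea, nausea, yeast vaginitis"). Risks to Research Participants says that potential reactions to the challenge "include skin rash, nausea, vomiting, diarrhea, and very rarely anaphylaxis".

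**Starting condition.** The screening criteria admit inpatients on "antibiotic therapy for an infection". They exclude "Patients who have been vomiting more than twice in the past 24 hours or are actively vomiting", and also critical illness, oxygen need, wheeze and stridor. They do not exclude current rash, diarrhea, nausea, or one or two vomiting episodes in the past day. Before dosing, "A set of baseline vital signs will be obtained by a trained study team member"; testing starts if these are normal and no contraindication is apparent.

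**Data and endpoint.** The primary endpoint in the Data Analysis Plan is verification of allergy status by challenge, analysed descriptively. The section on data to be collected covers identifiers, demographics, the recorded allergy status with any reaction description, PCP details and questionnaire answers. It names no challenge reaction type, dose step or time of onset.

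**The concern.** The endpoint is meant to verify allergy, but the rule behind it does not separate an allergic reaction from a drug side effect or from a symptom of the admission illness. A child labelled years ago for nausea is low-risk because nausea is non-immunologic. If nausea appears during the challenge and is recorded as a reaction, the same child fails and keeps the label. This does not depend on background illness, since a correctly attributed amoxicillin side effect would be classified the same way.

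For skin and GI findings, whether a child has developed something new cannot be checked afterwards if nobody recorded what was present before the first dose. The failure proportion is the obvious summary of the primary endpoint, and readers will set it against the roughly 10% truly allergic cited in the Background. Without a breakdown by type, that comparison has no clear meaning.

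**Working it through.** **Inputs from the documents.** About 60 enrolled of about 800 screened, taken from the ward census; there is no power or precision calculation to reproduce. About 10% of labelled patients truly allergic (Background). Observation to 120 minutes, single visit.

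**Assumptions, not in the documents.** All 60 are challenged (an upper bound). True reactor rate p is 5% or 10%. The rate b of unrelated or non-immunologic events counted as reactions within the window is 2%, 5% or 10%, independent of p.

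**Step 1: the failure rule alone.** Observed failure = 1 - (1 - p)(1 - b). Share of failures that are not true reactions = (observed - p) / observed. Example: p = 5%, b = 5% gives 1 - 0.95 × 0.95 = 9.75%, and (9.75 - 5) / 9.75 = 49%.

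| p | b | Observed failure | Expected failures of 60 | Of these, not true reactions | Share |
|---|---|---|---|---|---|
| 5% | 2% | 6.9% | 4.1 | 1.1 | 28% |
| 5% | 5% | 9.75% | 5.9 | 2.9 | 49% |
| 5% | 10% | 14.5% | 8.7 | 5.7 | 66% |
| 10% | 2% | 11.8% | 7.1 | 1.1 | 15% |
| 10% | 5% | 14.5% | 8.7 | 2.7 | 31% |
| 10% | 10% | 19.0% | 11.4 | 5.4 | 47% |

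The same observed 14.5% arises from p = 5% with b = 10% and from p = 10% with b = 5%, so the failure rate alone cannot tell them apart.

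**Step 2: could the data reveal it?** With p = 10% and b = 0, 6 of 60 fail, exact 95% CI 3.8-20.5%. The 14.5% expected with b = 5% lies inside that interval. A pilot of this size could not detect the inflation from the rate; it has to be handled in data capture.

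**Step 3: net direction.** Let m be the share of true reactors who react only after 120 minutes. Then observed = 1 - (1 - p(1 - m))(1 - b). Setting this equal to p gives the break-even b = pm / (1 - p(1 - m)).

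| m | Break-even b, p = 10% | Break-even b, p = 5% |
|---|---|---|
| 25% | 0.025 / 0.925 = 2.7% | 0.0125 / 0.9625 = 1.3% |
| 50% | 0.05 / 0.95 = 5.3% | 0.025 / 0.975 = 2.6% |
| 75% | 0.075 / 0.975 = 7.7% | 0.0375 / 0.9875 = 3.8% |

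Below these values the net result understates true reactivity; above them it overstates it. Late reactions are relevant here because the low-risk definition expressly includes children whose earlier reaction began more than 24 hours after exposure.

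**The case against.** The wording is tied to the drug. Step 6 speaks of signs or symptoms of a drug reaction and of something the patient develops, so a symptom already present is not a failure on a fair reading. A reader might infer that any symptom at all within two hours fails the child; the text does not say that, and the two-hour limit comes from the pass rule, not from the failure sentence. This stands.

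A reader might also infer that the challenged children already have rash or GI symptoms. No passage says so. Several exclusions reduce the chance, and a trained team member is at the bedside for 30 minutes after each dose. This stands too, but the exclusions leave gaps and bedside observation is not a recorded baseline.

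The failure sentences do not name nausea or diarrhea, and the list in the risk section is not a failure definition. Children with a non-immunologic history are still tested, not delabeled outright. The conflict is thus one of classification: the failure rule has no exception for events that the protocol elsewhere calls non-immunologic.

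The chart note must specify the reaction, so some split could be made later. That helps with type, but gives no baseline, and no stated plan carries it into the study data. Appendices A to E and the definition of terms are not available here. The latter is cited only for anaphylaxis, but either could hold a definition of reaction.

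Finally, a two-way split would not work: rash and vomiting appear in neither the immunologic nor the non-immunologic examples, and a child stopped at the 10% step has not had the full dose. This is right, and it is why an indeterminate class is needed.

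**Conclusion.** The point holds as one of endpoint definition and data capture. As written, the challenge-failure proportion may mix immunologic reactions with non-immunologic or illness-related events, and the planned data would not allow them to be separated reliably. With assumed true rates of 5-10% and assumed unrelated-event rates of 2-10%, observed failure would be about 7-19%, with 15% to 66% of failures not true reactions. These figures show sensitivity to the assumptions; they are not estimates for this trial.

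A reader might go further and conclude that the primary result overstates allergy. The documents do not support that. They give no background event rate. A failure means that the label is kept and referral advised, not that allergy is confirmed. Reactions after 120 minutes pull the other way. Two opposing errors of unknown size leave the proportion uninterpretable as true allergy, with the net direction open.

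**What to change.** 1. Reconcile the low-risk definition, the step 6 failure rules and the risk section on what counts as a reaction for the endpoint. If an appendix or the definition of terms already settles this, cite it in the Data Analysis Plan.
2. With the baseline vital signs, record skin, GI and respiratory findings.
3. Add REDCap fields for reaction type, dose step and minutes from dose; the chart note already specifies the reaction.
4. Keep any reaction as the as-run failure result. Beside it, report failures as immunologic-type, non-immunologic and indeterminate, each as a proportion of children challenged with an exact 95% CI. Indeterminate would cover, for example, rash or vomiting that the protocol's terms do not place, or a challenge stopped before the full dose.
5. State that non-immunologic and indeterminate failures are not counted as verified non-allergic.

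This concerns classification and reporting only. Bedside handling of a reaction and decisions on the label are not addressed. The cost is a short check at a visit already being made, a few database fields and a few table rows. The downside is some judgement in classifying reactions.

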	allergy label on EMR with previous reaction suggestive of anaphylaxis OR
	requiring hospitalization/epinephrine administration for the reaction OR reactions
	considered immunologic (angioedema, joint pains) OR involving serious types of
	reactions such as Steven-Johnson syndrome (SJS), toxic epidermal necrolysis
	(TEN), acute interstitial nephritis (AIN), drug-induced hepatitis or other
	documented organ injury, drug rash eosinophilia systemic symptoms (DRESS),
	hemolytic anemia, drug-induced cytopenia, and serum sickness. Patients who were
	previously diagnosed with penicillin allergy by an allergist also belong to the high-
	risk group.

Number of Research Participants

We will screen approximately 800 patients and enroll approximately 60 patients in our study based on the weekly census of Rainbow 3, 5 and 6 floors over a span of 6 months (September 22, 2021– March 31, 2022).

Recruitment Methods

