- 5. Patients identified in the high-risk group will not undergo oral amoxicillin challenge testing. Patients in this group that have not been evaluated by an allergist will be referred to Allergy/Immunology (AI) for further evaluation and management. A clinical event note will be written in the chart to document that the patient is identified to have reactions highly compatible with true penicillin allergy by history/screening and that referral was made to AI (see Appendix C.2).
- 6. Patients identified in the low-risk group will undergo a step-wise amoxicillin oral challenge testing. An extensive anticipatory guidance and explanation to parent/s or legal guardian about the steps of the testing as well as the risks of the procedure will be done prior to initiation of testing. Informed consent from a parent/s or legal guardian of the patient will be obtained to be able to proceed with testing. Assent will be obtained from patients 7-13 years of age.

Before initiating the step-wise oral amoxicillin challenge testing, it will be ensured that these patients have not taken any antihistamine in the previous 48 hours. Any patients with receipt of antihistamine in the previous 48 hours cannot undergo the testing and will be excluded.

The step-wise oral amoxicillin challenge allergy testing will ONLY be conducted during the day shift from 8:00AM-2:30 PM to make sure adequate medical personnel is present should untoward event occurs. Patients who have any of the exclusion criteria will not be eligible to proceed with the challenge testing (see exclusion criteria).

The following criteria also need to be met in order for the challenge testing to be performed:

- Parent/s or legal guardian present during the test
- A medical provider is available on the floor
- Rescue medications (refer to materials/appendix D ordered and available at bedside prn)

Only patients in the low-risk group who can tolerate enteral amoxicillin will be eligible to proceed to the step-wise oral amoxicillin challenge testing. This step will entail amoxicillin oral challenge test (either by mouth, by nasogastric tube or gastric tube). Patients not able to take the amoxicillin enterally will be excluded. A separate consent form will need to be signed for the oral amoxicillin challenge testing part of the study.

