If the patient did not have any reaction to the remaining 90% of standard dose at 120 minutemark following start of challenge testing, then the patient is deemed to not have allergy to penicillin. The allergy label in the EMR will then be removed with a notation "patient underwent direct oral amoxicillin challenge testing with no reaction on (date)". The patient's vital signs will again be obtained by a trained study team member and recorded for documentation (see Appendix C.4).

The pediatric ID fellow will be present for 30 minutes following each dose of amoxicillin. The study team attending or the pediatric ID fellow will also oversee study team members who are still in residency training through direct supervision during critical portions of the procedure (within 30 minutes of challenge dose administration). The pediatric ID fellow will always be available in person within the campus for the resident team members for every patient challenged throughout the entire duration of the challenge testing. Anytime a patient is challenged, the pediatric ID fellow will be present not more than 3-5 minutes away from the study site and always reachable by a dedicated study team phone. Study team members will also be responsible to attend/respond to any reaction the patient may have that is related to the oral challenge testing procedure.

All vital signs obtained throughout the procedure will be performed and recorded by trained study team members. Administration of the graded enteral amoxicillin doses and rescue medications if indicated will also be performed by the study team members.

7. The result of the oral challenge testing be communicated to the patient's primary care physician for guidance on future use of penicillin in the form of a letter that will be handed to the parent/s or guardian containing the result of the challenge testing. Permission will be obtained from parent/s or guardian before communication of result to PCP. Permission will be obtained during the consent process. Education on the patient's change in allergy status will then be provided to the parents.

Study Timeline

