Costs to Research Participants

The cost of the delabeling procedure will be free to the patient/s. This would otherwise be a relatively expensive procedure if done in an allergist's clinic. The cost of the challenge medications (amoxicillin) will be billed to the patient/s insurance as these are medications used in standard of practice allergy delabeling process and as this study entails standard of practice delabeling procedure. If the patient/s will develop reaction to the challenge testing, the cost of the rescue medications will be part of the patient's standard of care cost and will be billed to the patient/s insurance as well.

Research Participant Compensation

There will be no compensation, in any form, given to research participants.

Provisions to Monitor the Data to Ensure the Safety of Research Participants

Data collection will take place at UH RBC premises. Data will be managed by the PI ([name]) and coinvestigators ([name], [name], [name], [name] and [name]) using REDCap database. REDCap (Research Electronic Data Capture) is a secure web application for building and managing online surveys and databases. Only the study PI ([name]) and study team members will have access to identifiable private information. The study team will monitor at least every 1- 2 weeks for accuracy and adherence to protocol.

Drugs and Devices

Amoxicillin – standard full dose is 45 mg/kg/dose (maximum total dose 1000 mg) – to be given only by enteral route (naso-gastric tube, oro-gastric tube, gastric-tube) in two graded doses: 10% initial dose and 90% dose.

Indication: "Challenge Dose Amoxicillin" in order

Diphenhydramine - 1 mg/kg PO or IV (maximum dose 50 mg) – 12.5 mg/5 ml formulation and 50 mg/vial preparation

Albuterol – 2.5 mg/3ml nebule

Oxygen – to be given by nasal cannula to maintain oxygen saturation more than 92 %

Normal saline (0.9 % NaCL IV solution) - 20 ml/kg as bolus as needed for hypotension

Epinephrine 1:1000 for rescue medication:

<50 kg: Epinephrine (1mg/mL) at 0.01 mg/kg/dose – will be given as Epinephrine Jr 0.15 mg/0.3 ml auto-injector

>50 kg: Epinephrine (1mg/mL) at 0.5 mg/dose – will be given as Epinephrine 0.3 mg/0.3 ml autoinjector

Additional Information

Please see attached protocol algorithm (Appendix A), screening questionnaire (Appendix B) and clinical event notes (Appendix C).

References

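### The rescue epinephrine lines contradict themselves: the auto-injector named for each weight band does not deliver the dose printed beside it

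*Combined protocol and SAP*

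**What the plan says.** The Drugs and Devices section lists epinephrine 1:1000 as a rescue drug in two weight bands, each joining a dose to a product.

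- Below 50 kg: "<50 kg: Epinephrine (1mg/mL) at 0.01 mg/kg/dose – will be given as Epinephrine Jr 0.15 mg/0.3 ml auto-injector".
- Above 50 kg: "at 0.5 mg/dose – will be given as Epinephrine 0.3 mg/0.3 ml autoinjector".

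Under Study Procedures Methods, step 6, one condition for starting a challenge reads "Rescue medications (refer to materials/appendix D ordered and available at bedside prn". If anaphylaxis develops after either the 10% or the 90% amoxicillin dose, "epinephrine will be administered right away either by IV or IM (see Appendix D", and "Administration of epinephrine will be done by a trained study team member". These procedural paragraphs give no epinephrine dose of their own. The text available gives no repeat-injection rule, no rounding rule and no other device. Appendix D was not available for this review.

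**The concern.** Each line gives a dose and then names the product that will supply it, so the two figures should agree. Above 50 kg one flat dose is paired with a different flat dose. Below 50 kg a dose that rises with weight is paired with a device that cannot vary, across a band that runs up to 50 kg. Eligible patients are 3 to 18 years old with no weight limit, so body weight will range widely.

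At stake is the treatment of a child who has anaphylaxis caused by the study procedure. Study staff give the epinephrine themselves, and bedside rescue medication is one of the protections named under Risks to Research Participants. Anyone above 15 kg treated with a single injection from this list would receive less than the dose printed on the same line.

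**Working it through.** **Inputs, all from Drugs and Devices.** Below 50 kg: 0.01 mg/kg, device 0.15 mg in 0.3 ml. Above 50 kg: 0.5 mg, device 0.3 mg in 0.3 ml. Both lines give the concentration as 1 mg/mL. The protocol gives no body weights, so the weights in the table are illustrative assumptions. The 60% figure and the 15 kg match do not depend on them.

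**Above 50 kg.** Device ÷ stated dose = 0.3/0.5 = 0.60, a shortfall of 0.5 − 0.3 = 0.20 mg. Repeat injections do not reach the printed dose either: one gives 0.3 mg and two give 0.6 mg.

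**Below 50 kg.** The device matches the stated dose where 0.15 = 0.01 × weight, that is, at 0.15/0.01 = 15 kg. Elsewhere the share delivered is 0.15/(0.01 × weight):

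| Weight (kg) | Stated dose (mg) | Device (mg) | Share delivered | Difference (mg) |
|---|---|---|---|---|
| 12 | 0.12 | 0.15 | 125% | +0.03 |
| 15 | 0.15 | 0.15 | 100% | 0 |
| 20 | 0.20 | 0.15 | 75% | −0.05 |
| 30 | 0.30 | 0.15 | 50% | −0.15 |
| 40 | 0.40 | 0.15 | 37.5% | −0.25 |
| 49 | 0.49 | 0.15 | 31% | −0.34 |

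The device is within 10% of the stated dose only from 0.15/(1.1 × 0.01) = 13.6 kg to 0.15/(0.9 × 0.01) = 16.7 kg.

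**At the 50 kg boundary.** The stated doses join smoothly: 0.01 × 50 = 0.5 mg, the same as the flat dose above. The device dose doubles there: 0.30/0.15 = 2.

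**Would a different device cut-off reconcile the lines?** With the 0.15 mg device below cut-off *c* and the 0.3 mg device from *c* upward, the share of 0.01 mg/kg is 15/*c* just below it and 30/*c* at it. That gives 75% and 150% at *c* = 20 kg, 60% and 120% at 25 kg, and 50% and 100% at 30 kg. No cut-off makes two fixed devices follow 0.01 mg/kg.

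**Two minor points.** Exactly 50 kg falls in neither band. The smaller device contains 0.15/0.3 = 0.5 mg/mL, not the 1 mg/mL printed on its line; this is a labelling slip that adds no dosing error.

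**The case against.** The strongest reply is that under-dosing of a participant has not been shown. The procedures send staff to Appendix D, which may carry correct or repeat doses, and rescue drugs are ordered before each challenge. The procedures also allow IV epinephrine, which an auto-injector does not suit, so another presentation may be intended. This stands as a limit on the consequence: what a child would actually receive depends partly on a document not seen. It does not rescue the two lines. A correct Appendix D would then conflict with the drug list.

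A second reply is that fixed-dose injectors are a practical approximation to weight-based dosing. That is fair for small differences, such as those at 12 or 20 kg, and the number of children near 50 kg is unknown. It does not explain delivering about 31% of the stated dose near the top of the band, and it has no bearing on a flat 0.5 mg given as 0.3 mg.

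A third reply is that the exposure is small and well guarded. The plan is "We will screen approximately 800 patients and enroll approximately 60 patients in our study", only low-risk patients are challenged, and the listed reactions "include skin rash, nausea, vomiting, diarrhea, and very rarely anaphylaxis". Also, "The pediatric ID fellow will be present for 30 minutes following each dose of amoxicillin". Staff are trained by a pediatric allergy attending, a provider must be on the floor, oxygen, albuterol and saline are listed, a rapid response or code is called when indicated, and patients are watched for two hours after epinephrine. All of this lowers the chance and the consequences of an event, but none of it makes the printed doses agree. The challenge is read out at 120 minutes, and the fellow's stated presence covers 30 minutes after each dose; otherwise the fellow may be 3 to 5 minutes away.

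**Conclusion.** The concern holds, and the text must be corrected on patient-safety grounds. The drug list specifies two different epinephrine doses in each band: 0.3 mg against 0.5 mg above 50 kg (60%), and a fixed 0.15 mg against 0.01 mg/kg below it, exact only at 15 kg. The percentages compare one injection with one stated dose. Confidence is high that the lines conflict. Whether a child would be under-dosed in practice depends on Appendix D and on what is stocked at the bedside. The documents do not show which element is mistaken: the doses, the devices or the 50 kg cut-off. No endpoint, sample size or analysis is affected.

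**What to change.** Amend the two epinephrine lines, and Appendix D to match, so that each weight band has one dose that the named product delivers.

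- **Preferred:** draw up 0.01 mg/kg, maximum 0.5 mg, from the 1 mg/mL solution. This keeps both printed doses and the printed concentration, and it removes the boundary problem because 0.01 × 50 = 0.5. It needs vials and syringes at the bedside.
- **Alternative:** keep the auto-injectors, restate the doses as 0.15 mg and 0.3 mg, and move the device cut-off well below 50 kg, to a weight set by the allergist co-investigator and pharmacy. This needs both devices at the bedside. It makes the text consistent only by accepting 0.3 mg above 50 kg, 0.20 mg less than now printed, and it still only approximates 0.01 mg/kg below that weight. If chosen, the protocol should say so openly.

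Under either option, assign exactly 50 kg to a band if bands remain, print each product's own concentration, and state which presentation is for IM use and which, if any, is for IV use. The cost is a short amendment and a check of Appendix D, with no change to sample size or analysis.
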